### Purpose of Study

Women who receive epidural analgesic during labor often experience hypotension, typically within the first 30 minutes after epidural placement. This maternal low blood pressure can impact blood flow to the infant which is seen through decreases in the infant's heart rate. The current study aims to evaluate whether elevating patients' legs on a peanut ball for the first 40 minutes after epidural placement will decrease the incidence of maternal hypotension and fetal heart rate decelerations.

### Hypothesis or Research Question

- Hypothesis 1: Laboring women who receive epidural analgesia and elevate their legs on a peanut ball will experience a lower incidence of requiring intervention for low blood pressure compared to laboring women who receive epidural analgesia and do not elevate their legs.
- Hypothesis 2: Laboring women who receive epidural analgesia and elevate their legs on a peanut ball will experience a lower incidence of hypotension compared to laboring women who receive epidural analgesia and do not elevate their legs.  
\*hypotension is defined as SBP < 90 mmHg or an SBP decreases more than 20% from baseline
- Hypothesis 3: Infants of laboring women who receive epidural analgesia and elevate their legs on a peanut ball will experience a lower incidence of late or prolonged decelerations compared to laboring women who receive epidural analgesia and do not elevate their legs.

## Background

Aortocaval compression (ACC) by the gravid uterus is a known physiological phenomenon that is claimed to cause supine hypotension in full term pregnant patients. ACC has been noted as a possible cause of post-spinal hypotension (PSH). Hypotension is defined as a systolic blood pressure of less than 90mmHg or a diastolic blood pressure of less than 60mmHg. The left tilt is the usual solution to remedy the hypotension for laboring women. Maternal physiologic changes such as increased blood volume has an impact on the circulation system: low maternal blood pressure can result in decreased perfusion of the placenta. This negatively impacts maternal blood flow to the fetus which is noted on the fetal monitor as a Category II or III fetal heart tracing. While hypotension may not cause problems in some women, the fetus in utero is accustomed to and dependent on a certain blood pressure threshold.

A peanut labor ball (PB) is a non-latex, plastic, air-filled yoga ball that is shaped like a peanut. It is used during labor for maternal pain relief and maternal position changes. The goal of using the PB is to shorten the duration of labor by keeping open the laboring woman's pelvic floor and to decrease the incidence of cesarean sections or medical -assisted vaginal deliveries, by the use of forceps and vacuums, among women who receive epidural anesthesia.

The purpose of this study is to examine the effectiveness of elevating a woman's legs on a PB in preventing hypotension among a sample of laboring women who receive an epidural analgesia.

## Research Plan

- **Study Design**

This study will use a randomized, non-blinded, controlled design with two arms:

- Arm 1 (Intervention): Immediately after epidural placement, patient will be placed in a left tilt position with her hip on a wedge and both of her legs elevated on an orange peanut ball. She will remain in this position for approximately 40 minutes.
- Arm 2 (Control/Standard Care): Immediately after epidural placement, patient will be placed in a left tilt position with her hip on a wedge. She will remain in this position for approximately 40 minutes.

- **Setting for the study**

The study will take place on Good Samaritan Hospital's Labor and Delivery Unit. This unit consists of 20 labor rooms and provides care to approximately 11 laboring women each day.

- **Participants**

The study will enroll 300 women who meet the following inclusion/exclusion criteria:

Inclusion Criteria:

- Laboring at Good Samaritan Hospital Labor & Delivery Unit
- 37+ weeks gestation
- Planned vaginal delivery
- Planned epidural analgesia

Exclusion Criteria:

- Under 18 years old
- Does not speak English
- Unable to consent to involvement in the research study
- Attended less than 3 prenatal care office visits
- Diagnosed with fetal demise
- Diagnosed with fetal anomalies
- Contraindications to both legs being elevated (ex: fractured bones, lower limb amputation, etc.)
- Contraindications to receiving 1L of IV fluids
- Requiring IV hypertensive medications
- Requiring IV magnesium

Sample Size Determination: A power analysis was conducted using a dichotomous outcome variable, requiring intervention for low blood pressure, with an expected difference [(33% incidence rate (Auroy et al., 1997), clinical significance would be a decrease to 15%)] (0.2), power of 0.8, and level of significance 0.05. It was determined that 120 patients would be needed in each group, for a total sample size of 240 patients. To allow us to also examine the impact on occurrence of infant decelerations and to allow for the possibility of removing participants from the final analysis due to missing data, we plan to enroll 300 patients (150 in each group).

- **Data Collection**

Before the study begins, information about the study will be provided to the nurses on the L&D unit including education about the study purpose, inclusion/exclusion criteria, and procedures.

When a patient who meets the inclusion/exclusion criteria is admitted, a nurse will describe the study, answer any questions the patient has, and if the patient wants to enroll in the study, the study team nurse will review the information consent form. After the patient provides written informed consent, the nurse will remove the next envelope out of a box of prefilled and sealed opaque envelopes. The envelope will provide the Subject ID number to be used on all study-related documentation and the study Arm that the patient has been randomized to, either:

1. Leg Elevation Group
2. Standard Care Group

These envelopes will be filled using a computerized simple random number generator (1:1 randomization) prior to the start of the study.

In addition to the group assignment, the envelope will include a data collection form. Data will be recorded directly on this form during the patient's visit. The form will collect the following information:

- Whether patient was assigned to the leg elevation group or the standard care group
- Patient age
- Pregnancy history
- Height
- Weight
- Whether pregnancy is a singleton or multiple pregnancy
- Blood pressure documented at last prenatal office visit
- Threshold systolic blood pressure (20% decrease from office visit blood pressure) – The study team nurse will calculate threshold systolic blood pressure by calculating the systolic blood pressure from most recent office visit multiplied by 0.8
- Time of epidural placement
- Time legs elevated on peanut ball (Intervention group only)
- Time legs removed from peanut ball (Intervention group only)
- Did the infant have any late or prolonged decelerations within the 1 hour after epidural placement? Yes/No
- Did the RN have to perform any interventions to address prolonged or late decelerations during the 1 hour after epidural placement? Yes/No
- Did the anesthesia provider treat the maternal blood pressure during the 1 hour after epidural placement? Yes/No

RN will complete the data collection form and place the signed informed consent form and data collection form in a locked room designated for study materials.

On the data collection forms, RNs are instructed to call a member of the study team immediately if there are any safety concerns related to the leg elevation. If the study team receives a call about a safety concern, recruitment and enrollment of new participants will stop until the study team meets and reviews the incident and determines it is safe to continue. Any adverse events and serious adverse events will be reported to the IRB in compliance with IRB safety policies.

- **Intervention or experimental aspect of the study**

After epidural placement, nurse will verify that patient received 1L of IV fluid and had Category I fetal heart tracing in the one hour prior to epidural placement. If

either of these aren't met, patient will be removed from study and no further procedures will take place.

If patient received 1L of IV fluid and had Category I fetal heart tracing in previous 1 hour, patients randomized to Arm 1 will be placed in a left tilt position with a hip wedge. Next both legs will be elevated on an orange peanut ball. the epidural placement. Their legs will be lowered approximately 40 minutes after after epidural placement. Peanut ball use during labor is a standard practice on this unit. The intervention will involve using the peanut ball for leg elevation

Patients randomized to Arm 2 will receive standard care. After epidural placement, they will be placed in a left tilt position with a hip wedge. Patient will remain in this position for 40 minutes after epidural placement.

After the 40 minutes of positioning or leg elevation, the next blood pressure obtained will be documented on the data collection form and then the study procedures are completed.

- **Statistical Analysis**

Data recorded on paper data collection forms will be entered into a password protected database. Only study team members will have access to the database. No personal information will be entered into the electronic database. Data will undergo range checks when entered into the database, and quality control procedures will be performed to ensure accuracy of the data in the electronic database.

Statistical analyses will be performed using Intellectus Statistics statistical software. The following analyses will be performed to address each hypothesis:

Hypothesis 1: Laboring women who receive epidural analgesia and elevate their legs on a peanut ball will experience a lower incidence of requiring intervention for low blood pressure compared to laboring women who receive epidural analgesia and do not elevate their legs.

*To compare the effects of leg elevation, a Chi Square test will be used to compare occurrence of receiving intervention for low blood pressure for patients who elevated their legs to patients who did not elevate their legs. A level of significance of  $\alpha=0.05$  will be used.*

Hypothesis 2: Laboring women who receive epidural analgesia and elevate their legs on a peanut ball will experience a lower incidence of hypotension compared to laboring women who receive epidural analgesia and do not elevate their legs.

*To compare the effects of leg elevation, a Chi Square test will be used to compare occurrence of maternal hypotension for patients who elevated their legs to*

*patients who did not elevate their legs. A level of significance of  $\alpha=0.05$  will be used.*

Hypothesis 3: Infants of laboring women who receive epidural analgesia and elevate their legs on a peanut ball will experience a lower incidence of late or prolonged decelerations compared to laboring women who receive epidural analgesia and do not elevate their legs.

*To compare the effects of leg elevation, a Chi Square test will be used to compare occurrence of late or prolonged infant decelerations for patients who elevated their legs to patients who did not elevate their legs. A level of significance of  $\alpha=0.05$  will be used.*

Interim data analysis will occur (1) once approximately 1/3 of the participants have been enrolled and (2) once approximately 2/3 of the participants have been enrolled. If interim calculations at time (1) or time (2) note a significant difference between groups in maternal hypotension or frequency of late or prolonged fetal decelerations, data collection will be completed at that time and final analysis will be completed.

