## Results

A randomized controlled trial was conducted with patients enrolled between October 29, 2022 and May 29, 2025. Patients were enrolled if they were at least 37 weeks gestation, laboring at Good Samaritan Hospital labor and delivery unit, planned to have epidural analgesia, and planned to have a vaginal delivery. They were excluded if they were under 18 years old, did not speak English, were unable to provide informed consent, attended less than 3 prenatal care office visits, were diagnosed with fetal demise, were diagnosed with fetal anomalies, had contraindications to both legs being elevated, had contraindications to receiving 1L of IV fluids, required IV hypertensive medications, or required IV magnesium.

A total of 104 patients were consented. Patients were randomized using a simple random number generator (1:1 randomization) into one of two study arms:

- Arm 1: Leg Elevation group (n=58)
- Arm 2: Standard Care group (n=44)
- 2 changed mind before randomization

Several patients in each arm were removed from the study before completion, resulting in **92 patients** who completed study:

- Arm 1: Leg Elevation group (n=58 consented - 4 removed = 54 completed study)
  - Delivered before epidural placed (1)
  - Had Category II tracings after consent signed and before epidural placed (2)
  - Breech and had c-section (1)
- Arm 2: Standard Care group (n=44 consented - 6 removed = 38 completed study)
  - Emergency c-section before epidural placement (1)
  - Had Category II tracings after consent signed and before epidural placed (3)
  - Didn't have 1L fluid bolus administered (2)

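### The stated 120 per group for 80% power does not follow from 33% vs 15% at 0.05; those inputs need 88 per group (98 with continuity correction)

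*Combined protocol and SAP*

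**What the plan says.** The only sample-size justification is the Sample Size Determination paragraph under Research Plan, Participants. The outcome is binary: whether the mother needed treatment for low blood pressure. The control rate is 33%, and the remaining inputs follow: "clinical significance would be a decrease to 15%)] (0.2), power of 0.8, and level of significance 0.05". The conclusion is "It was determined that 120 patients would be needed in each group, for a total sample size of 240 patients".

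The next sentence adds a separate allowance, partly for the deceleration outcome. Its other purpose is stated as "to allow for the possibility of removing participants from the final analysis due to missing data, we plan to enroll 300 patients (150 in each"; the bracket gives the number per arm.

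Three other places bear on the calculation:

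- **Test.** Statistical Analysis, Hypothesis 1: "a Chi Square test will be used to compare occurrence of receiving intervention for low blood pressure", at 0.05. It does not say one-sided or two-sided.
- **Direction.** Hypothesis 1 is worded directionally: leg-elevated women "will experience a lower incidence of requiring intervention for low blood pressure".
- **Allocation.** The Data Collection text specifies 1:1 randomisation.

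**The concern.** Apart from sidedness and the exact formula, the paragraph gives everything needed to recompute the number: two proportions, power, significance level and, from elsewhere, the test and the allocation ratio. The standard calculation gives a figure well below 120, and the gap is too large to be rounding or a choice between textbook formulas. The value (0.2) after the two rates adds doubt: it has no label, and the stated rates differ by 0.18.

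What is at stake is the written justification. A reader cannot reproduce it, and it attaches the wrong power to 120 per group. It also sets the yardstick for judging the achieved sample. The Results section reports 92 completers. That is 38% of 240 (92/240), but 47–52% of the 176–196 that the stated inputs call for (92/196 and 92/176). The trial fell short either way, but by an amount the current text misdescribes.

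**Working it through.** **Inputs.** p1 = 0.33, p2 = 0.15, power 0.80 and alpha 0.05 from Sample Size Determination; chi-square test from Statistical Analysis; 1:1 allocation from Data Collection. Two-sided testing is inferred from the chi-square test; one-sided is shown as well.

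**Formula.** With d = p1 − p2 = 0.18 and mean rate 0.24,

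n = [z(α)·√(2·0.24·0.76) + z(power)·√(p1(1−p1) + p2(1−p2))]² / d²

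The two roots are √0.3648 = 0.6040 and √(0.2211 + 0.1275) = √0.3486 = 0.5904.

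**Two-sided.** n = (1.960·0.6040 + 0.8416·0.5904)² / 0.0324 = (1.1838 + 0.4969)² / 0.0324 = 87.18, so 88 per group (176 in total).

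Continuity correction: (n/4)·[1 + √(1 + 4/(n·d))]² = (87.18/4)·[1 + √1.2549]² = 97.98, so 98 per group (196 in total).

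**Trying to reproduce 120 from the stated rates, power and level:**

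| Variant | Per group |
|---|---|
| Two-sided, pooled variance | 88 |
| Two-sided, continuity corrected | 98 |
| One-sided, pooled variance | 69 |
| One-sided, continuity corrected | 80 |
| Two-sided, unpooled variance | 85 |
| Two-sided, arcsine | 86 |
| Fisher's exact test | 98 gives 80.5% power |

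**Trying the 0.2:**

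- As an absolute difference: 33% vs 13% needs 69, and 35% vs 15% needs 73. The maximum over all pairs 20 points apart is 97, at 60% vs 40% (107 corrected).
- As Cohen's w on 1 df: 197 in total, about 99 per group. The stated rates give w = 0.09/√(0.24·0.76) = 0.21.
- As Cohen's h: 393 per group.

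**Inputs that do land near 120.** Each of these uses something the paragraph does not state. The list is not exhaustive.

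- 90% power, two-sided: 117.
- 95% power, one-sided: 120.
- Alpha 0.05/3: 117.
- A Pocock level for three looks (about 0.0221) with continuity correction: 119.85, so 120.
- 59% vs 41%: 119.9, so 120.
- w = 0.2 on 2 df: 241 in total. A two-by-two table has 1 df.

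The origin of 120 therefore cannot be established.

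**Power at the planned numbers, 33% vs 15%, two-sided, single look.** At 120: z = (0.18·√120 − 1.1838)/0.5904 = (1.9718 − 1.1838)/0.5904 = 1.335, so power is 0.909.

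| Analysed per group | Uncorrected | Corrected | Exact, Pearson | Exact, Fisher |
|---|---|---|---|---|
| 120 | 0.909 | 0.881 | 0.914 | 0.887 |
| 150 | 0.958 | 0.944 | 0.960 | 0.948 |

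The 150 row holds only if all 150 are analysed at one look. The extra 30 are there partly to absorb missing data. A patient without the fluid load or the required fetal tracing "patient will be removed from study and no further procedures will take place", which under this protocol happens after randomisation. Two interim looks are also planned: "Interim data analysis will occur (1) once approximately 1/3 of the participants have been enrolled", and again at about two thirds.

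**The case against.** The best defence is that 120 may be a sound figure from an undocumented method. The paragraph speaks of an expected difference. If only the 18-point difference was used, with the rates placed symmetrically about one half where the variance is greatest (59% vs 41%), the two-sided answer at the stated power and level is 119.9, so exactly 120. That is a closer candidate than 90% power, which contradicts the stated 0.8 and gives 117. It may well be what happened. It does not make the paragraph correct, because it sets aside the 33% control rate that the paragraph cites, and nothing in the text says it was done.

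A second defence is an unstated allowance for interim looks or for three hypotheses, which can also reach about 117–120. The paragraph gives a plain 0.05 and mentions neither, and Statistical Analysis repeats 0.05 for each hypothesis.

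Third, the matter has little practical weight: 120 per group more than meets the 80% target, and recruitment is over. The Results section reports 104 consented and notes: "Several patients in each arm were removed from the study before completion". Both observations stand. They limit the severity and confine the remedy to the written record, but the stated number still does not follow from its inputs.

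**Conclusion.** The point holds and is minor. From 33% vs 15%, 80% power and significance level 0.05, the requirement is 88 analysed patients per group, or 98 with continuity correction. The stated 120 is 22 to 32 more per group, 44 to 64 in total. At a single look 120 per group carries about 91% power, or about 88–89% with continuity correction or Fisher's exact test.

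This rests on two-sided testing, which is inferred; one-sided testing widens the gap. It also assumes 1:1 allocation and one analysis at the full number. The arithmetic is certain; the reason for 120 is unknown. The error is conservative, so no planned power was lost and none of the reported comparisons is affected.

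**What to change.** Correct the paragraph in the record and in any later report. Suggested wording:

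> For 33% vs 15%, chi-square test, two-sided alpha 0.05 and a single look, 120 analysed patients per group give about 91% power (about 88–89% with continuity correction or Fisher's exact test); 80% power needs 88 analysed per group (98 with continuity correction).

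Name the formula and the sidedness. Replace the bare 0.2 with a labelled effect: difference 0.18, Cohen's w 0.21. If a power is quoted for 150 per group, say that about 96% assumes all 150 are analysed at a single look. If other inputs produced 120, such as a maximum-variance calculation for the 18-point difference or 90% power, state those instead.

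The cost is a text edit. The planned enrolment figure, the interim looks and the analyses need no change on this account.

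### Hypothesis 2 takes its baseline from an office visit and no pre-epidural blood pressure is recorded, so a pressure that was already low can be counted as post-epidural hypotension; one added reading would allow a check

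*Combined protocol and SAP*

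**What the plan says.** Under Hypothesis or Research Question, the event for Hypothesis 2 is given as "hypotension is defined as SBP < 90 mmHg or an SBP decreases more than 20% from baseline". Baseline is not defined there.

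The form items under Research Plan, Data Collection supply the only working reference. They list "Blood pressure documented at last prenatal office visit" and then "Threshold systolic blood pressure (20% decrease from office visit blood pressure", calculated as the office SBP times 0.8. No admission or pre-epidural pressure is listed.

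Under Research Plan, Intervention, the step before positioning is that the "nurse will verify that patient received 1L of IV fluid and had Category I fetal heart tracing in the one hour prior to epidural placement". Blood pressure is not part of that check, and no eligibility criterion concerns low pressure before the epidural. The one later pressure mentioned comes after the 40 minutes, when "the next blood pressure obtained will be documented on the data collection form and then the study procedures are completed".

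The Statistical Analysis section plans an unadjusted chi-square test. It also lets a significant difference in maternal hypotension at either interim look end data collection.

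**The concern.** The question is about hypotension that follows the epidural: the Purpose of Study says that these women "often experience hypotension, typically within the first 30 minutes after epidural placement". To attribute a low reading to that period, one needs to know that the pressure was not already low when the period began.

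The plan applies this reasoning to the fetal outcome. A woman stays in the study only if she "had Category I fetal heart tracing in the one hour prior to epidural placement", and the Results show five women removed for Category II tracings (two and three by arm). Maternal pressure, the subject of Hypothesis 2, has no counterpart. Nothing listed can separate a new fall from a pressure that was already under 90 mmHg or under 0.8 times the office value.

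At stake are the reading of Hypothesis 2 as an incidence after the epidural and, because this outcome feeds the stopping rule, the interim decisions.

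**Working it through.** **1. The reported result.** The Results give 13% of 54 and 21% of 38, which correspond to 7/54 and 8/38. Pearson chi-square without continuity correction gives 1.07, p = 0.30, as reported.

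**2. How many women could be affected.** The documents give no figure, so every input here is an assumption: office SBP mean 118, SD 11; pre-epidural SBP higher by 0, 5 or 10 mmHg on average; SD of the individual change 10 to 15. An SBP meets the definition if it is below the larger of 90 and 0.8 × office SBP. Simulating 2 million women per case gives this share already below threshold before the epidural:

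| Mean rise | SD 10 | SD 12 | SD 15 |
|---|---|---|---|
| 0 mmHg | 3.3% | 5.2% | 8.6% |
| 5 mmHg | 1.4% | 2.4% | 4.8% |
| 10 mmHg | 0.5% | 1.1% | 2.5% |

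The range is about 0.5% to 9%. The middle case of 2.4% is about 2 of the 92 women (0.024 × 92 = 2.2).

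**3. Average effect on the comparison.** Let q be the share already below threshold. Assume that these women are balanced across arms, stay below threshold and are unaffected by leg elevation. An arm with new-onset rate p then shows q + (1 − q)p, and the risk difference d becomes (1 − q)d. The plan states no planning rates for Hypothesis 2, so I take 21% v 10% as illustrative new-onset rates. (The 21% is borrowed from the reported control rate, which would already contain any pre-existing cases.) For q = 3%: control 0.03 + 0.97 × 0.21 = 0.234; leg elevation 0.03 + 0.97 × 0.10 = 0.127; difference 0.107 instead of 0.110.

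Power uses the two-sided 5% normal approximation, with pooled variance under the null:

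| q | Difference | Power, 150 v 150 (planned) | Power, 54 v 38 (analysed) |
|---|---|---|---|
| 0% | 11.0 points | 75% | 32% |
| 2.4% | 10.7 points | 69% | 28% |
| 3% | 10.7 points | 67% | 27% |
| 6% | 10.3 points | 60% | 24% |

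**4. If leg elevation does help some of these women.** Suppose it lifts a fraction r of them above threshold. The difference becomes (1 − q)d + qr, which equals d when r = d. So if r exceeds 11% (or 18%, using the Hypothesis 1 planning rates of 33% v 15%), there is no dilution.

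**5. Chance imbalance in the reported data.** Removing hypothetical already-low women from both numerator and denominator gives:

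| Removed (leg elevation, standard care) | Event rates | p |
|---|---|---|
| 0, 0 | 7/54 v 8/38 | 0.30 |
| 2, 2 | 5/52 v 6/36 | 0.33 |
| 4, 3 | 3/50 v 5/35 | 0.20 |
| 3, 0 | 4/51 v 8/38 | 0.07 |
| 0, 2 | 7/54 v 6/36 | 0.62 |

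Splits that are even, or nearly so, change little. Lopsided splits of two or three women change a lot, in either direction.

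**The case against.** The strongest objection is that the office reading is a reasonable reference. The Background says that "the fetus in utero is accustomed to and dependent on a certain blood pressure threshold", which supports comparing with a habitual pressure. That stands, and it is why the office threshold should be kept. It also disposes of a related complaint. With an office SBP of 118 the threshold is 94.4, so a woman at 128 or 138 before the epidural must fall by 26% (33.6/128) or 32% (43.6/138) to count. That follows from choosing a habitual reference and is not an error.

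A reader might go further and infer that already-low women are counted whatever leg elevation does, add equally to both arms, and so explain the null result for Hypothesis 2. The documents do not support this:

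- They do not say that such women were enrolled, and they do not state how a Hypothesis 2 event is ascertained. Such a woman counts only if she is still low at whatever reading is used, after 1 L of fluid and left tilt.
- Nothing says that leg elevation cannot raise a low pressure.
- Balance holds only in expectation, and the analysed arms are 54 and 38.
- At those numbers power is about 32% even with no pre-existing cases, against 28% at q = 2.4%. The small sample is a sufficient reason for a non-significant result.

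It is also fair that reclassifying events after results are reported, in a non-blinded trial, would not be sound as the main analysis.

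**Conclusion.** The point holds as a cheap improvement. Baseline is undefined in Hypothesis 2 and becomes the office reading on the form, and no pre-epidural SBP is listed, checked or used for adjustment. Low pressure that predates the epidural and persists can therefore be counted as an event, under the 90 mmHg limb as well as the 20% limb.

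The likely average direction is toward no difference, provided that these women are balanced across arms and unaffected by leg elevation. The size cannot be taken from the documents; about 0.5% to 9% of women rests wholly on the assumed pressures in the working. At the middle of that range the average effect is small. The stronger reason to act is that 15 events are few enough for a chance imbalance of two or three women to move p to 0.07 or 0.62, and the listed data cannot show whether one occurred.

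**What to change.** 1. State in Hypothesis 2 that baseline means the last prenatal office SBP.
2. Add one form field in both arms, the last charted SBP before epidural placement with its time, completed at the existing fluid and tracing check. The envelope has been opened by then, so a charted value is preferable to a reading chosen by a nurse who knows the arm. It still precedes positioning, so leg elevation cannot affect it.
3. Keep the office-based chi-square as the main analysis.
4. Add (a) an analysis of Hypothesis 2 adjusted for pre-epidural SBP, for example logistic regression on arm and that reading only, given few events; and (b) a sensitivity analysis that excludes women already below threshold before the epidural from both numerator and denominator. Report their number by arm.
5. For the 92 completed women, take the reading from the chart where it exists and report the result as a post hoc sensitivity analysis beside the published comparison.

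The cost is one field, or a look-up in 92 charts. Some readings may be missing, since the documents do not establish that one is charted routinely, and the sensitivity analysis will have slightly fewer women and events. The change adds a measurement and alters neither eligibility nor care.

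### The arm is allocated before the fluid and tracing checks that decide who stays in this open-label trial; opening the envelope after the checks would close that route to bias

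*Combined protocol and SAP*

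**What the plan says.** - Research Plan, Study Design: "This study will use a randomized, non-blinded, controlled design with two arms". Positioning follows at once in both arms: "Immediately after epidural placement, patient will be placed in a left tilt position with her hip on a wedge".
- Research Plan, Data Collection: "After the patient provides written informed consent, the nurse will remove the next envelope out of a box of prefilled and sealed opaque envelopes". Inside are the Subject ID and the arm. The form is there too: "In addition to the group assignment, the envelope will include a data collection form".
- Research Plan, Intervention or experimental aspect of the study. The two checks are described as follows: "After epidural placement, nurse will verify that patient received 1L of IV fluid and had Category I fetal heart tracing in the one hour prior" (that is, before the epidural). If either condition fails, "patient will be removed from study and no further procedures will take place".
- Research Plan, Statistical Analysis: each chi-square test compares outcomes "for patients who elevated their legs to patients who did not elevate their legs". No analysis population is defined, and nothing says that removed women are followed up or that the person making the checks is unaware of the arm.
- Results: 58 and 44 women are listed by arm, 4 and 6 were removed, and 54 and 38 completed. Two further women withdrew before randomisation and are listed separately.

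**The concern.** Randomisation protects a comparison only if entry to the analysis cannot depend on the arm. Here a filter is applied after allocation by staff who may know the arm. They could affect it in three ways: by whether the litre is given in time, by how the tracing is judged, and by whether a failed check leads to removal.

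Fluid given and tracing category are plausibly related to later low blood pressure and decelerations. Arm-dependent removal could therefore bias the comparison in either direction, and with only 92 women analysed a few removals can move a p-value visibly.

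The list of form items in Data Collection names no field for either check. That list is not complete, because the plan later adds that "the next blood pressure obtained will be documented on the data collection form". The gap therefore does not show that the checks went unrecorded.

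**Working it through.** **1. Order of events.** Data Collection does not say when the envelope is opened. Results settles that allocation came first: one woman listed under leg elevation delivered before an epidural, and one listed under standard care had an emergency cesarean before an epidural. Both had an arm before the post-epidural checks could take place.

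**2. Removals, from Results.**

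| Reason | Leg elevation (58) | Standard care (44) |
|---|---|---|
| Category II tracing | 2 | 3 |
| 1L not given | 0 | 2 |
| Check failures, subtotal | 2 (3.4%) | 5 (11.4%) |
| Delivery or cesarean | 2 | 1 |
| Total removed | 4 | 6 |
| Analysed | 54 | 38 |

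Fisher exact test, two-sided, on check failures 2/58 vs 5/44: p=0.23.

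**3. Reproducing the reported Hypothesis 1 result.** Results gives 11% vs 29%. The only counts out of 54 and 38 that round to these are 6 (11.1%) and 11 (28.9%). With a=6, b=48, c=11, d=27 and N=92:

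X² = N(ad − bc)² / [(a+b)(c+d)(a+c)(b+d)] = 92 × (162 − 528)² / (54 × 38 × 17 × 75) = 12,323,952 / 2,616,300 = 4.71, p=0.030.

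This matches the document. The risk difference is 11.1 − 28.9 = −17.8 points.

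**4. Restoring the seven check failures.** Assume that all seven had an epidural, so that the hour after it exists for them. The groups become 56 and 43. Added events can be 0–2 and 0–5, giving 3 × 6 = 18 possible outcomes. The extremes are:

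| Leg elevation | Standard care | Difference (points) | Chi-square p |
|---|---|---|---|
| 6/56 | 16/43 | −26.5 | 0.0017 |
| 8/56 | 11/43 | −11.3 | 0.157 |

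If none of the seven had an event (6/56 vs 11/43), p=0.052.

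**5. Restoring only the two women without 1L.** Results can also be read as saying that the five Category II women left before any epidural. The groups are then 54 and 40:

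| Leg elevation | Standard care | Difference (points) | Chi-square p |
|---|---|---|---|
| 6/54 | 11/40 | −16.4 | 0.041 |
| 6/54 | 12/40 | −18.9 | 0.021 |
| 6/54 | 13/40 | −21.4 | 0.011 |

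The other three removals are not restored. Two of these women had no epidural, so the outcome window never began, and the timing of the breech cesarean is not stated.

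**6. Effect of later opening.** Seven check failures plus the two women who delivered or had a cesarean before an epidural make 9 of the 10 removals. These would have been screen failures before randomisation.

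**The case against.** The removal rule was written in advance, is the same in both arms, and concerns the period before positioning. The removal pattern is weak evidence: Category II removals alone are 2/58 vs 3/44 (Fisher p=0.65), and the rest of the difference is two women. Knowledge of the arm is itself inferred. Keeping the data form inside the envelope makes early opening likely, but the documents do not say who knew. All of this stands, and it limits the point to an open route.

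Three stronger readings are tempting, and the documents do not support them.

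- *The unequal removals show bias.* They are compatible with chance, and no figure for arm-dependent removal is given or can be derived.
- *The restored p-values measure the bias.* They do not. With the later opening, women failing the checks would also be outside the analysis. If the checks were applied evenly, 54 vs 38 is the kind of group the improved design would analyse. Nor can a probability be put on the 18 outcomes by giving removed women the event rates of retained women, since the concern is that they may differ.
- *The Hypothesis 1 result was fragile anyway, because Fisher (0.054) and Yates (0.058) exceed 0.05.* The plan names a chi-square test, and the smallest expected count is 38 × 17/92 = 7.0, which meets the usual rule for the uncorrected test.

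It is also fair to say that enrolment is described in the past tense and that removals by arm and reason are already reported. The design change therefore cannot repair this dataset.

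**Conclusion.** The point holds as a weakness in the order of steps. Allocation precedes checks that decide who is analysed, in an open-label trial, with no follow-up of those removed. It is a cheap improvement to make, not a demonstration that the result is biased.

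On the outcome in Results, Hypothesis 1, leaving out randomised women matters to this extent: p moves from 0.030 to between 0.0017 and 0.157 with all seven check failures restored, or to between 0.011 and 0.041 with only the two no-1L women restored. Leg elevation has the lower rate in every case.

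This rests on the inferred counts 6/54 and 11/38. The wider range also assumes that all seven women had an epidural. The outcome used is broader than the planned one: Results counts nurse or physician intervention for hypotension or late decelerations, while the Hypothesis section and Statistical Analysis specify intervention for low blood pressure. The figures describe the reported composite only.

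**What to change.** **For further enrolment or a successor protocol**
- Keep consent at admission.
- Record both checks on a form held outside the envelope.
- Open the next sealed envelope only after the epidural is placed and both checks are passed and recorded.
- Analyse every woman whose envelope was opened in her assigned arm, and word the tests as women randomised to leg elevation against women randomised to standard care.

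**For the existing data**
- Add an all-randomised sensitivity analysis covering the full range of outcomes in both directions. First state whether it uses the planned outcome or the reported composite.
- State whether the five Category II women had an epidural.
- State that removed women have no reported outcomes.

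**Cost.** Low. No check is added, because the plan already places both between epidural and positioning. The Subject ID and data form must be handled apart from the arm assignment, and consented women who are never randomised need a log. The plan must say who holds and opens the envelope, and the peanut ball must be at hand before the arm is known. Opening adds a brief step before positioning that the plan calls immediate; the documents give no duration for it. Open-label recording of outcomes and interventions remains and needs its own safeguard.
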